6. TREATMENT PLAN

This is a phase II window of opportunity trial in which women with a diagnosis of DCIS, LCIS, ALH or ADH will be treated with rapamycin at 2 mg/day for 5-7 days. Surgery will be performed 3-7 days after the last dose of rapamycin. An evaluable patient for toxicity is any patient who has received at least 1 dose of rapamycin. An evaluable patient for efficacy is any patient who has completed at least 5 days of rapamycin therapy and has had surgery within the 7-day window.

7. STUDY DRUG ADMINISTRATION

Study drug will be given orally once a day in the form of tablets. Patient may take drug consistently with or without food.

8. TOXICITIES AND ADVERSE REACTIONS

Rapamune[®]

The incidence of adverse reactions was determined in two randomized, double-blind, multicenter controlled trials in which 499 renal transplant patients received Rapamune Oral Solution 2 mg/day, 477 received Rapamune Or I Solution 5 mg/day, 160 received azathioprine, and 124 received placebo. All patients were treated with cyclosporine and corticosteroids. Data (\geq 12 months post-transplant) presented in the table below show the adverse reactions that occurred in any treatment group with an incidence of \geq 20%.

Specific adverse reactions associated with the administration of Rapamune (sirolimus) Oral Solution occurred at a significantly higher frequency than in the respective control group. For both Rapamune Oral Solution 2 mg/day and 5 mg/day these include hypercholesterolemia, hyperlipemia, hypertension, and rash; for Rapamune Oral Solution 2 mg/day acne; and for Rapamune Oral Solution 5 mg/day anemia, arthralgia, diarrhea, hypokalemia, and thrombocytopenia. The elevations of triglycerides and cholesterol and decreases in platelets and hemoglobin occurred in a dose-related manner in patients receiving Rapamune.

Patients maintained on Rapamune Oral Solution 5 mg/day, when compared with patients on Rapamune Oral Solution 2 mg/day, demonstrated an increased incidence of the following adverse events: anemia, leukopenia, thrombocytopenia, hypokalemia, hyperlipemia, fever, and diarrhea. In general, adverse events related to the administration of Rapamune were dependent on dose/concentration.

9. DOSE MODIFICATIONS

No dose modifications will be allowed.

10. CONCOMMITANT MEDICATIONS

All concomitant treatments, including blood and blood products, must be reported on the appropriate electronic case report form (eCRF).

10.1 Not Permitted

Patients who are taking any herbal (alternative) medicines are NOT eligible for participation. Patients must be off any such medications before the first dose of study treatment. Patients who are undergoing concomitant radiotherapy or chemotherapy are NOT eligible for participation.

10.2 Permitted

Supportive care, including but not limited to anti-emetic medications, may be administered at the discretion of the treating physician.

11. DURATION OF THERAPY

Treatment duration is 5-7 days

12. FOLLOW-UP POST-THERAPY

Patients will be followed 3 months after surgery at the time of routine clinic visit or via phone call with study personnel, See APPENDIX 3 –subsection titled Research Chart (case report form needed for data collection during this 3-month follow-up visit).

Treatment after study completion will be left to the discretion of the treating physician(s) and will not be considered part of this study. However, patients should still be followed for surgical complications as part of their standard of care.

Procedures	Screening & Baseline	Day 1-7 ⁴	Day before Surgery	Surgery ²	3 month Follow-Up
Tissue procurement ¹				Х	
Informed consent	х				
Rapamycin administration		Х			
Cancer history ³	х		х		
Physical exam ³	х		х		
CBC w/ diff	X ³		Х		
Comprehensive metabolic panel	X ³		х		
Lipid panel	х		х		
Estradiol ⁵	Х		х		
FSH⁵	Х		х		
Toxicity (AE) assessment			Х		Х

13. SCHEDULE OF EVENTS

¹ Fresh tissue procurement will be required for study purposes.

² Surgery can take place 3-7 days after completion of rapamycin treatment

- ³ Pre-study laboratory tests, cancer history, and physical exam (including review of systems) must be completed within 28 days prior to registration. At the discretion of the treating physician and only if clinically indicated as part of their standard of care, the pre-study CBC and CMP will be repeated one (1) day prior to treatment administration.
- ⁴ Rapamycin will be administered for 5-7 days
- ⁵ Estradiol and FSH are required only if patient is under 60 years of age and has not had a bilateral oophorectomy.

14. DRUG FORMULATION AND PROCUREMENT

Rapamune[®] (sirolimus) is an immunosuppressive agent. Sirolimus is a macrocyclic lactone produced by *Streptomyces hygroscopicus*. The chemical name of sirolimus (also known as rapamycin) is (3*S*,6*R*,7*E*,9*R*,10*R*,12*R*,14*S*,15*E*,17*E*,19*E*,21*S*,23*S*,26*R*,27*R*,34a*S*)-9,10,12,13,14,21,22,23,24,25,26,27,32, 33,34,34a-hexadecahydro-9,27-dihydroxy-3-[(1*R*)-2-[(1*S*,3*R*,4*R*)-4-hydroxy-3-methoxycyclohexyl]-1-methylethyl]-10,21-dimethoxy-6,8,12,14,20,26-hexamethyl-23,27-epoxy-3*H*-pyrido[2,1-c][1,4]

oxaazacyclohentriacontine-1,5,11,28,29(4*H*,6*H*,31*H*)-pentone. Its molecular formula is C51H79NO13 and its molecular weight is 914.2. The structural formula of sirolimus is shown below. The inactive ingredients in Rapamune[®] Tablets include sucrose, lactose, polyethylene glycol 8000, calcium sulfate, microcrystalline cellulose, pharmaceutical glaze, talc, titanium dioxide, magnesium stearate, povidone, poloxamer 188, polyethylene glycol 20,000, glyceryl monooleate, carnauba wax, *dl*-alpha tocopherol, and other ingredients. The 2 mg dosage strength also contains iron oxide yellow 10 and iron oxide brown 70.

14.1 Mechanism Of Action

Rapamycin inhibits T lymphocyte activation and proliferation that occurs in response to antigenic and cytokine (Interleukin [IL]-2, IL-4, and IL-15) stimulation by a mechanism that is distinct from that of other immunosuppressants. Rapamycin also inhibits antibody production. In cells, rapamycin binds to the immunophilin, FK Binding Protein-12 (FKBP-12), to generate an immunosuppressive complex. The rapamycin:FKBP-12 complex has no effect on calcineurin activity. This complex binds to and inhibits the activation of the mammalian Target Of Rapamycin (mTOR), a key regulatory kinase. This inhibition suppresses cytokine-driven T-cell proliferation, inhibiting the progression from the G1 to the S phase of the cell cycle. Studies in experimental models show that rapamycin prolongs allograft (kidney, heart, skin, islet, small bowel, pancreatico-duodenal, and bone marrow) survival in mice, rats, pigs, and/or primates. Rapamycin reverses acute rejection of heart and kidney allografts in rats and prolongs the graft survival in presensitized rats. In some studies, the immunosuppressive effect of rapamycin lasts up to 6 months after discontinuation of therapy. This tolerization effect is alloantigen specific. In rodent models of autoimmune disease, rapamycin suppresses immune-mediated events associated with systemic lupus erythematosus, collagen-induced arthritis, autoimmune type I diabetes, autoimmune myocarditis, experimental allergic encephalomyelitis, graft-versus-host disease, and autoimmune uveoretinitis.

14.2 PRECAUTIONS

14.2.1 General

Rapamune[®] is intended for oral administration only.

Lymphocele, a known surgical complication of renal transplantation, occurred significantly more often in a dose-related fashion in patients treated with Rapamune[®]. Appropriate operative measures should be considered to minimize this complication.

14.2.2 Lipids

The use of Rapamune[®] in renal transplant patients was associated with increased serum cholesterol and triglycerides that may require treatment. In Studies 1 and 2, in *de novo* renal transplant recipients who began the study with normal, fasting, total serum cholesterol (<200 mg/dL) or normal, fasting, total serum triglycerides (<200 mg/dL), there was an increased incidence of hypercholesterolemia (fasting serum cholesterol >240 mg/dL) or hypertriglyceridemia (fasting serum triglycerides >500 mg/dL), respectively, in patients receiving both Rapamune[®] 2 mg and Rapamune[®] 5 mg compared with azathioprine and placebo controls. Treatment of new-onset hypercholesterolemia with lipid-lowering agents was required in 42 - 52% of patients enrolled in the Rapamune[®] arms of Studies 1 and 2 compared with 16% of patients in the placebo arm and 22% of patients in the azathioprine arm.

In Study 4 (cyclosporine withdrawal study) during the prerandomization period, mean fasting serum cholesterol and triglyceride values rapidly increased, and peaked at 2 months with mean cholesterol values > 240 mg/dL and triglycerides > 250 mg/dL. After randomization mean cholesterol and triglyceride values remained higher in the cyclosporine withdrawal arm compared to the Rapamune[®] and cyclosporine combination. Renal transplant patients have a higher prevalence of clinically significant

hyperlipidemia. Accordingly, the risk/benefit should be carefully considered in patients with established hyperlipidemia before initiating an immunosuppressive regimen including Rapamune[®].

Any patient who is administered Rapamune[®] should be monitored for hyperlipidemia using laboratory tests and if hyperlipidemia is detected, subsequent interventions such as diet, exercise, and lipid lowering agents, as outlined by the National Cholesterol Education Program guidelines, should be initiated. In clinical trials, the concomitant administration of Rapamune[®] and HMG-CoA reductase inhibitors and/or fibrates appeared to be well tolerated. During Rapamune[®] therapy with cyclosporine, patients administered an HMG-CoA reductase inhibitor and/or fibrate should be monitored for the possible development of rhabdomyolysis and other adverse effects as described in the respective labeling for these agents.

14.3 ADVERSE REACTIONS

Rapamune® Oral Solution: The incidence of adverse reactions was determined in two randomized, double-blind, multicenter controlled trials in which 499 renal transplant patients received Rapamune® Oral Solution 2 mg/day, 477 received Rapamune® Oral Solution 5 mg/day, 160 received azathioprine, and 124 received placebo. All patients were treated with cyclosporine and corticosteroids. Data (> 12 months post-transplant) presented in the table below show the adverse reactions that occurred in any treatment group with an incidence of \geq 20%. Specific adverse reactions associated with the administration of Rapamune[®] (sirolimus) Oral Solution occurred at a significantly higher frequency than in the respective control group. For both Rapamune[®] Oral Solution 2 mg/day and 5 mg/day these include hypercholesterolemia, hyperlipemia, hypertension, and rash; for Rapamune[®] Oral Solution 2 mg/day acne; and for Rapamune[®] Oral Solution 5 mg/day anemia, arthralgia, diarrhea, hypokalemia, and thrombocytopenia. The elevations of triglycerides and cholesterol and decreases in platelets and hemoglobin occurred in a dose-related manner in patients receiving Rapamune®. Patients maintained on Rapamune[®] Oral Solution 5 mg/day, when compared with patients on Rapamune[®] Oral Solution 2 mg/day, demonstrated an increased incidence of the following adverse events: anemia, leukopenia, thrombocytopenia, hypokalemia, hyperlipemia, fever, and diarrhea. In general, adverse events related to the administration of Rapamune[®] were dependent on dose/concentration.

14.4 Storage

Rapamune[®] Oral Solution bottles should be stored protected from light and refrigerated at 2°C to 8°C (36°F to 46°F). Once the bottle is opened, the contents should be used within one month. If necessary, the patient may store the bottles at room temperatures up to 25°C (77°F) for a short period of time (e.g., not more than 15 days for the bottles). An amber syringe and cap are provided for dosing and the product may be kept in the syringe for a maximum of 24 hours at room temperatures up to 25°C (77°F) or refrigerated at 2°C to 8°C (36°F to 46°F). The syringe should be discarded after one use. After dilution, the preparation should be used immediately.

Rapamune[®] Oral Solution provided in bottles may develop a slight haze when refrigerated. If such a haze occurs allow the product to stand at room temperature and shake gently until the haze disappears. The presence of this haze does not affect the quality of the product. Rapamune[®] tablets should be stored at 20° to 25°C (USP Controlled Room Temperature) (68° to 77°F). Use cartons to protect blister cards and strips from light. Dispense in a tight, light-resistant container as defined in the USP.

15. STATISTICAL CONSIDERATIONS

15.1 Study Population

This study proposes recruitment of women with DCIS, LCIS, ALH or ADH cases. The population in the San Antonio area are mostly Hispanics (~55%) and Caucasian (~45%).

15.2 Statistical and Data Analysis

Availability of case and justification of sample size. According to our co-investigator and breast pathologist, the surgeons at our cancer center operated 24 cases of DCIS in 2013.

Ages	# of patients at UT Health San Antonio Mays Cancer Center
< 50	7
50-59	10
> 60	7

We consider about 60-70% enrollment in 5-year recruitment duration, we shall be able to recruit about 50-60 patients with menopausal status clinically confirmed. Tissue from this study will be compared to DCIS specimens from patients not treated with rapamycin. These specimens will be collected through the ongoing biorepository.

Statistically significant differences of the histopathological parameters and the molecular markers between the core biopsy and surgical specimens due to the rapamycin treatment will be tested by Mantel-Haenszel test for categorical data with scores ranging from 0 to 4 (or higher) as shown in Figure 2. To reach statistical power >70%, a patient group size of 24 or more is required for us to detect the difference of a score of 0.3 between untreated biopsy and treated surgical specimens with the P value targeted at 0.05 for one-sided Mantel-Haenszel test.

The **Mantel-Haenszel test** (between Rapamycin treatment & non-participant patients) will be set up as follows.

No Rapamycin # of patients (c) # of patients (d) c/(c+d)

Test between treatment & non-participant patients				
Study		IHC score ≤ 2	IHC score > 2	Percentage
UT Health San Antonio	Rapamycin	<pre># of patients (a)</pre>	# of patients (b)	a/(a+b)

Mantel-Haenszel test will allow us to extend IHC score to full range (instead of dichotomizing the IHC score), as well as other sites if more patients will be enrolled at different sites (we will not lump all patients together into one group, in case the underlying population demographic is a concern at different enrollment sites). Significance will be determined at p-value < 0.05 (Chi-square distributed with one degree of freedom). During the recruitment period, we will monitor the IHC scores different from two groups (treated/untreated) with simple *t* test on average IHC score (across all patients within each group) for each marker, in order to assess the IHC effectiveness, enrollment progress and patient demographic parameters and their association to final study outcomes.

For statistical test within either treatment or control arm, we will use **McNemar's test** to examine IHC score differences between biopsy and surgical tissues (at significance level of 0.05). The 2x2 table set up as follows.

Test within treatment or no treatment

After treatment

		IHC score ≤ 2	IHC score > 2
Before treatment	IHC score ≤ 2	# of patients with	# of patients with
		lower IHC scores before & after	higher IHC score after treatment
	IHC score > 2	# of patients with	# of patients with
		lower IHC score after treatment	higher IHC scores before & after

Similar to between arm test, during the recruitment period, we will monitor the IHC scores different within each arm with simple paired-*t* test on average IHC score difference for each marker, in order to assess the IHC effectiveness, enrollment progress and patient demographic parameters and their association to final study outcomes.

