APPENDIX 4 – List of prohibited strong CYP3A4 inducers and inhibitors	

1. SYNOPSIS

Title	g Mammary Stem Cells and Breast Cancer Prevention		
Design	Design Non-randomized, open-label, phase II, window of opportunity trial.		
	The overall purpose of this study is to determine if rapamycin can reduce malignant markers and MaSC number in surgical specimens.		
Objectives	 The primary objectives are: Reduction of MaSC in DCIS, LCIS, ALH or ADH in patients receiving rapamycin Reduction of malignant markers in DCIS, LCIS, ALH or ADH in patients 		
	receiving rapamycin The secondary objectives are: 1. Toxicity 2. Surgical complications		
Patient Population	Women (pre and post-menopausal) with DCIS, LCIS, ALH or ADH undergoing surgical resection.		
Treatment Plan	Women who consent will be given rapamycin for 5-7 days treatment at 2 mg/day. Patients will undergo mastectomy or lumpectomy 3-7 days after the last dose of rapamycin. Pathological and molecular biomarkers associated with breast cancer aggressiveness and recurrence will be assessed by the Breast Pathologist and the features of MaSCs will be determined by the PI's lab for determining the effect of rapamycin.		
Efficacy Assessment	Efficacy will be measured by measurement of MaSC and malignant markers in tissue from patients with DCIS, LCIS, ALH or ADH		

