5. PATIENT ELIGIBILITY

5.1 Inclusion Criteria

Subjects must meet all of the following criteria to be eligible for the trial:

- 1. Women with confirmed menopausal status. All patients who have NOT had a prior bilateral oophorectomy and/or are younger than age 60, will require menopausal status verified by FSH and estradiol local labs.
- 3. Women diagnosed with DCIS, LCIS, ALH or ADH lesions detected by pathology
- 4. Women scheduled for mastectomy or lumpectomy after DCIS, LCIS, ALH or ADH diagnosis
- 5. Women consented to the tissue biorepository (HSC20070684H/CTRC# 07-32)

- 6. Women of child-bearing potential willing to practice 2 forms of contraception, one of which must be a barrier method until at least 30 days after the last dose of rapamycin.
- 7. Women of child-bearing potential must have a negative serum pregnancy test at time of enrollment.
- 8. Patients must be able to swallow and retain oral medication.
- 9. All patients must have given signed, informed consent prior to registration on study.
- 10. Patients must have normal organ and marrow function as defined below:
 - a. Leukocytes ≥ 3,000/µL
 - b. Absolute neutrophil count \geq 1,500/µL
 - c. Platelets \geq 100,000/µL
 - d. AST $\leq 2.5 \text{ X ULN}$
 - e. ALT $\leq 2.5 \text{ X ULN}$
 - f. Total bili \leq 1.5 X ULN or Direct bili \leq 1 X ULN

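### The comparison with untreated biorepository controls is not stratified by menopausal status, so a different pre/postmenopausal mix could mimic or hide a drug effect

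*Combined protocol and SAP*

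**What the plan says.** The Synopsis describes the design as "Non-randomized, open-label, phase II, window of opportunity trial" and the population as "Women (pre and post-menopausal) with DCIS, LCIS, ALH or ADH". Section 5.1, item 1, admits "Women with confirmed menopausal status" and specifies which women "will require menopausal status verified by FSH and estradiol local labs". The Schedule of Events (Section 13) marks estradiol and FSH at screening and again on the day before surgery. Its footnote 5 limits them: "Estradiol and FSH are required only if patient is under 60 years of age and has not had a bilateral oophorectomy".

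Section 15.2 projects recruitment in terms of status ("recruit about 50-60 patients with menopausal status clinically confirmed") and takes its controls from untreated DCIS specimens in the biorepository. It describes no matching on age or menopausal status and gives no control sample size. The planned tests are:

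- Mantel-Haenszel, treated versus non-participant patients, chi-square with 1 df at 0.05. Enrolment site is the only stratum named, and only if other sites join.
- McNemar, biopsy versus surgical tissue within each arm, at 0.05.
- Simple and paired t tests on mean IHC score, for monitoring during recruitment.

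None of these uses menopausal status, estradiol or FSH.

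**The concern.** Nothing in the design balances menopausal status between treated women and controls. Women who join the trial and women whose tissue happens to be in the biorepository may have a different pre/postmenopausal mix. If IHC scores or MaSC measures also differ by status, the unstratified comparison picks up the difference in mix along with any drug effect. The error can go either way: it can make an inactive drug look active, or mask an active one.

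The plan already accepts the principle, because it declines to pool sites in case their demographics differ. Menopausal status is a patient characteristic that the protocol makes an entry condition, yet it gets no stratum.

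A difference by status is plausible but not documented. The mouse data in Section 3 link age, not menopause, to MaSC frequency, p16 and COX2. The comparison with untreated women may also carry more weight for MaSC than for IHC: the Schedule of Events marks tissue procurement only at surgery, so it provides no paired pre-treatment fresh sample.

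**Working it through.** **1. The plan's own recruitment figure.** Section 15.2 states that surgeons "operated 24 cases of DCIS in 2013": 7 under 50, 10 aged 50-59 and 7 over 60. It assumes 60-70% enrolment over 5 years.

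- All cases: 24 x 5 x 0.60 to 0.70 = 72 to 84. This does not give 50-60.
- Cases aged 50 and over: 17 x 5 x 0.60 to 0.70 = 51 to 59.5. This does.

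The arithmetic suggests that the projection rests on the two older rows, leaving out 7/24 = 29% of cases. The text does not say so, and women under 50 remain eligible.

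**2. Which comparisons are exposed.**

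- Treated versus non-participant: different women in each group, so a difference in mix enters the contrast.
- Biopsy versus surgery within a woman: her status is the same at both points, so it cancels. The sizing statement (24 or more, a 0.3-point difference, power above 70%, one-sided 0.05) refers to this contrast.

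**3. Size of the bias.** For an unadjusted difference in mean score,

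bias = (difference in premenopausal share) x (score difference by status).

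Every input here is an assumption, because the documents give none of them: shares of 50% and 30%, a score difference of 0.5 to 1.0, a score SD of 1.0, and equal groups of 24 or 50.

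Bias = 0.20 x 0.5 to 0.20 x 1.0 = 0.10 to 0.20 points.

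With no drug effect, a two-sided 5% z-test rejects with probability P(|Z + m| > 1.96), where m = bias / (SD x sqrt(2/n)).

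| n per group | SD x sqrt(2/n) | m | Rejection rate |
|---|---|---|---|
| 24 | 0.289 | 0.35 to 0.69 | 6.4% to 10.7% |
| 50 | 0.200 | 0.50 to 1.00 | 7.9% to 17.0% |

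A smaller SD or larger imbalance raises these rates; equal shares return them to 5%.

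**4. Does stratifying remove it?** A separate simulation used the 2x2 layout in Section 15.2 (IHC score at or below 2 versus above 2), with no drug effect and 200,000 runs per scenario. The inputs are again assumed: the probability of a low score is 0.60 in postmenopausal women and 0.50, 0.40 or 0.30 in premenopausal women. Entries are two-sided rejection rates for the 1-df Mantel-Haenszel test over those three values.

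| Premenopausal, treated vs control | Crude, 24/group | Stratified, 24/group | Crude, 55/group | Stratified, 55/group |
|---|---|---|---|---|
| 30% vs 30% | 5.8-5.9% | 4.9-5.2% | 4.5% | 4.8-5.0% |
| 29% vs 50% | 6.0-8.3% | 4.9-5.1% | 5.0-9.2% | 4.9-5.0% |
| 0% vs 29% | 6.2-10.6% | 5.0% | 5.7-14.1% | 5.0% |
| 10% vs 50% | 6.7-15.0% | 4.8-5.0% | 6.4-22.8% | 5.0% |

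The first row shows what the crude test does without imbalance, so only the excess over that row is due to the mix. Stratifying holds the rate near 5% throughout, given that status is known and correctly classified in both groups.

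**The case against.** **The main comparison is untouched.** This stands. The paired tests are free of this bias. A reader might infer that the whole efficacy analysis is compromised, but the documents do not support that. Pooling the paired test over status could dilute an effect confined to one group; that is a matter of subgroup power, not bias.

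**The size is assumed.** This also stands. The z-test on means is not the dichotomised table that Section 15.2 displays, and the low end (6.4% against 5%) is small. A reader might set the 0.10 to 0.20 point bias against the 0.3-point difference in Section 15.2, but that target is set for biopsy versus surgery. The plan states no target for treated versus non-participant patients.

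**The plan already looks at demographics.** Section 15.2 does mention patient demographics and their association with outcomes. It does so as a monitoring aim attached to unadjusted t tests, with no stratum, covariate or model, so it does not answer the point.

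**Age could stand in for status, or age alone shows an imbalance.** A reader might take the hormone testing of women aged 50-59 as evidence on this. The documents give no reason for the testing, and it also covers women under 50. Nor does the recruitment arithmetic establish that treated women will be mostly postmenopausal.

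**Another mismatch is more certain.** Treated women may have DCIS, LCIS, ALH or ADH, while the controls are DCIS specimens. That is true, and stratifying by menopausal status leaves it in place. It is a separate issue and does not remove this one.

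**Conclusion.** The point holds for the treated-versus-non-participant Mantel-Haenszel test only. A variable required at entry is absent from an unmatched, non-randomised comparison that it could confound. Bias needs two conditions together, a different menopausal mix and a marker difference by status, and the documents quantify neither.

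Under the stated assumptions the false-positive rate of a nominal 5% test is 6.4-10.7% with 24 per group and 7.9-17.0% with 50 per group. These figures illustrate the mechanism; they are not estimates for this trial. A reader might conclude that an imbalance would necessarily be mistaken for a benefit. The direction is unknown, and the opposite imbalance would conceal one.

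This is a worthwhile, inexpensive improvement to one stated analysis. It does not undermine the within-patient tests or the n=24 statement.

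**What to change.** In Section 15.2:

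- Stratify the treated-versus-non-participant Mantel-Haenszel test by menopausal status (pre/post) as well as site.
- Take each control's status from her record, using one written definition that can be applied to both groups. If treated women are classified by hormone results and controls by chart history, the strata will not mean the same thing.
- Report how many controls have unknown status and state how they are handled.
- Report biopsy-to-surgery change by status as descriptive or supportive only.

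While writing the definition, reconcile Section 5.1, item 1, which joins the oophorectomy and age conditions with and/or, with footnote 5 of the Schedule of Events, which requires both.

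I would not use the change in estradiol as a covariate. It is measured after treatment, so adjusting for it may remove part of a drug effect, and footnote 5 requires it only in a selected subset.

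The cost is a few lines of text and a chart look-up for controls, with no new visits or samples. The documents do not say that the biorepository records hold menopausal status, so the look-up may be incomplete. Some strata will be sparse, and a stratum with women from only one group contributes nothing to the test. The simulation covers error rate, not power, so it does not show what stratifying costs in power.

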4.1 Primary Objective

- 1. Reduction of MaSC in DCIS, LCIS, ALH or ADH in patients receiving rapamycin
- 2. Reduction of malignant markers in DCIS, LCIS, ALH or ADH in patients receiving rapamycin

4.2 Secondary Objectives

- 1. Toxicity
- 2. Surgical complications

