18. SAMPLES FOR BIOMARKER EVALUATION

Fresh tissue will be collected from patients with DCIS, LCIS, ALH or ADH treated with rapamycin. Tissue will be processed for IHC staining of p16, COX2, and Ki-67 in the core biopsy following the procedures described by Kerlikowske et al (66). We will also do IHC for autophagy markers, Beclin1 and LC3, and TUNEL assay to determine how rapamycin treatment may alter autophagy and apoptosis in the DCIS lesions.

To determine the effect of short-term rapamycin treatment on histopathological biomarkers in DCIS. A pathologist will quantify histopathological parameters including lesion size, nuclear grade, and presence of necrosis in each patient's surgical specimens, as well as IHC for the markers including p16, COX2, and Ki-67.

Three specific parameters will be evaluated:

- 1. Luminal-to-basal epithelial ratio, which will examine the MaSC in both luminal and basal cells, and their ratio, in order to address whether this ratio will change during aging;
- 2. Basal and luminal stem/progenitor cell frequency, which will examine the percentage of cells that are capable forming spheres, and whether these frequencies will change during aging; and
- 3. 3D structure regeneration frequency in serial passages, which will examine the selfrenewal/regeneration capacity of the stem and progenitor cells that are capable of forming spheres in suspension culture and in 3D-ECM culture, and can re-form the spheres when the sphere-forming cells are dissociated and allowed to regenerate spheres.

All fresh tissue specimens will be delivered to [name] laboratory located at:

UT Health San Antonio [name] [contact]

APPENDIX 1 – Common Toxicity Criteria for Adverse Events

Toxicity will be graded according to the NCI's Common Toxicity Criteria for Adverse Events (CTCAE) version 4.03. The CTCAE version 4.03 can be accessed at the following link: http://evs.nci.nih.gov/ftp1/CTCAE/CTCAE 4.03 2010-06-14 QuickReference 5x7.pdf

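### The treated-versus-untreated IHC comparison sets four lesion types against untreated DCIS alone, so lesion type is confounded with rapamycin

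*Combined protocol and SAP*

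**What the plan says.** **Treated side.** The Synopsis defines the population as "Women (pre and post-menopausal) with DCIS, LCIS, ALH or ADH undergoing surgical resection". Section 15.1 repeats it: "This study proposes recruitment of women with DCIS, LCIS, ALH or ADH cases". Section 5.1 makes all four diagnoses eligible without a quota. Section 6 defines efficacy evaluability by days of dosing and timing of surgery, not by lesion. One of the two primary objectives in 4.1 is "Reduction of malignant markers in DCIS, LCIS, ALH or ADH in patients receiving rapamycin". Section 18 says "Fresh tissue will be collected from patients with DCIS, LCIS, ALH or ADH treated with rapamycin".

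**Untreated side.** Section 15.2 names the comparator: "Tissue from this study will be compared to DCIS specimens from patients not treated with rapamycin". These specimens come from the ongoing biorepository.

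**Tests.** The Mantel-Haenszel table in 15.2 has one row for rapamycin and one for no rapamycin. The only stratum mentioned is site: "we will not lump all patients together into one group, in case the underlying population demographic is a concern at different enrollment sites". Significance is p < 0.05 on a chi-square with one degree of freedom. A t test during recruitment is run "on average IHC score (across all patients within each group) for each marker". Separately, McNemar's test is used within each arm "to examine IHC score differences between biopsy and surgical tissues".

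**The concern.** Nothing in the plan restricts the treated side to DCIS, matches controls on lesion type, or stratifies or adjusts for it. LCIS, ALH and ADH specimens can therefore appear only in the rapamycin row. If those lesions score differently from DCIS on a marker such as p16, COX2 or Ki-67, the difference is attributed to the drug. Lower scores in the other lesions mimic a benefit, and higher scores hide one. For LCIS, ALH and ADH the between-group question has no like-for-like control at all.

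The plan already accepts the principle for site, where it declines to pool patients whose demographics may differ. It does not apply it to lesion type, where the imbalance is built in and the diagnosis is recorded at entry.

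Section 15.2 names no test for the MaSC measures. A treated-versus-untreated MaSC comparison made under the same sentence would carry the same mismatch.

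**Working it through.** **The plan's own figure.** Section 15.2 requires 24 or more patients for power above 70% to detect 0.3 score points, one-sided 0.05. It gives no SD, so the figure cannot be reproduced directly. Solving back with 1.645 + 0.524 = 2.169:

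- paired difference: SD = 0.3 × √24 / 2.169 = 0.678
- two independent groups of 24: SD = 0.678 / √2 = 0.479

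The plan defines the 0.3 for biopsy versus surgery. Using it between groups is an illustration.

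**Lesion mix.** The documents do not give it. The accrual basis counts DCIS only: 24 × 5 years × 60–70% = 72–84, above the stated 50–60. The two older age rows alone, 17 × 5 × 60–70% = 51–59.5, match it. This leaves the non-DCIS share open; it may be small.

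**False reduction.** Let f be the non-DCIS share of treated patients and d the amount by which those lesions score lower than DCIS. With no drug effect:

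- spurious difference = f × d
- SE = √[(SD² + f(1−f)d²)/n + SD²/n]
- P(false reduction) = 1 − Φ(1.96 − f·d/SE), nominally 2.5%

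Example with f = 0.30, d = 1, SD = 1, n = 24: difference 0.30, SE = √[(1 + 0.21)/24 + 1/24] = 0.303, P = 1 − Φ(1.96 − 0.99) = 16.6%.

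| f | d | f × d | n = 24 per group | n = 55 per group |
|---|---|---|---|---|
| 10% | 0.5 | 0.05 | 3.7% | 4.5% |
| 10% | 1.0 | 0.10 | 5.2% | 7.4% |
| 30% | 0.5 | 0.15 | 7.4% | 11.8% |
| 30% | 1.0 | 0.30 | 16.6% | 32.2% |
| 50% | 1.0 | 0.50 | 37.2% | 69.6% |

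The bias does not shrink with enrollment, so the error rate rises with n. Simulating the one-degree-of-freedom mean-score test (20,000 runs per scenario) gave 3.4% to 35.1% at n = 24 and 4.5% to 68.7% at n = 55 over the same rows. Comparing DCIS with DCIS, it stayed at 2.2–2.6%.

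**Dichotomized scale.** Take P(IHC > 2) as 0.50 in DCIS and 0.20 in the other types, again assumed. With 25% non-DCIS the treated proportion is 0.75 × 0.50 + 0.25 × 0.20 = 0.425; with 40% it is 0.38. The two-sided 5% test then rejects 8% and 13% of the time at 24 per group, and 12% and 24% at 55. Stratifying by lesion type returned the simulated rate to 4.7–5.2%.

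**Masking.** Suppose non-DCIS lesions score higher by d and the true between-group reduction is 0.3, with 24 per group, SD 0.479 and one-sided 0.05. Power = 1 − Φ(1.645 − (0.3 − f·d)/SE).

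- f = 0: SE 0.138, power 70%
- f = 10%, d = 0.5: SE 0.142, net difference 0.25, power 55%
- f = 30%, d = 0.5: SE 0.146, net difference 0.15, power 27%

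**The case against.** The strongest reply is that these are not the tests the plan powers. The sample size rests on a biopsy-to-surgery contrast. McNemar's test addresses that contrast, and in treated patients it compares each woman with herself across all four lesion types, free of this confounding. That stands and limits the weight of the point. But 15.2 also sets up the between-group test with its own table and significance rule, and that test is the planned direct contrast with untreated patients. The t test matters less: it serves monitoring and carries no decision rule.

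A DCIS-versus-DCIS comparison may have been intended. The case count is DCIS only, Section 18 words its histopathology aim for DCIS, and the table label for controls names no lesion type. The quoted sentence could equally be wording that was not updated when eligibility widened. Either reading is possible, but neither is written as a restriction, and Section 18 itself collects tissue from all four types.

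The magnitudes are assumed, and the two sets use different SDs. That also stands: they are illustrations and should not be read as one scenario. At SD 0.479 the false-reduction rates would be higher (5.4% rather than 3.7% in the first row at n = 24), so SD 1 does not inflate the point.

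Finally, the controls are non-randomized in any case. True, but lesion type is a known, recorded and removable confounder.

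**Conclusion.** The concern holds and should be fixed. As written, lesion type is confounded with rapamycin in the between-group Mantel-Haenszel test and the monitoring t test. The confounding is partial, because treated DCIS patients do have untreated DCIS controls, and it does not reach the treated arm's McNemar test. That conclusion follows from the text and needs no assumed figure.

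Size and direction are unknown. The bias is zero if no non-DCIS patients enroll or if the lesion types do not differ on a marker. Under the assumed shares and gaps above it ranges from slight to as large as the planned effect: a 30% share with a 1-point gap gives 0.30.

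**What to change.** In 15.2, state that the treated-versus-untreated Mantel-Haenszel test and the monitoring t test compare treated DCIS with untreated DCIS. Where the biorepository holds untreated LCIS, ALH or ADH tissue, those types may be added with lesion type as a Mantel-Haenszel stratum alongside site. Report lesion types without untreated tissue only as within-patient biopsy-to-surgery IHC change, and limit the between-group conclusion to the lesion types compared.

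The DCIS-only option is a wording change and needs no new tissue. Its cost is fewer treated patients in the between-group test. Power = 1 − Φ(1.645 − 0.3/[0.479 × √(1/(n(1−f)) + 1/n)]):

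| Non-DCIS share | n = 24 per group | n = 55 per group |
|---|---|---|
| 0% | 70% | 95% |
| 10% | 68% | 94% |
| 25% | 64% | 92% |
| 50% | 55% | 85% |

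To keep 24 treated DCIS patients, enrollment would be 24/(1−f), rounded up: 27, 32 or 48 at shares of 10%, 25% or 50%. The stratified option depends on biorepository holdings, which the documents do not give, and its strata could be sparse: 10% of 24 is about two patients across three lesion types. Either way the comparison stays non-randomized.
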